4.1.7 Handling of Missing Data for the Primary Efficacy Test

To provide a true ITT efficacy test, subjects lost-to-follow-up prior to Day 28 must be imputed. A multiple imputation (MI) (Rubin and Schenker 1991)³ strategy will be used in the primary efficacy test followed by a completers analysis and a tipping point analysis as sensitivity analyses that examine the robustness of the Missing at Random (MAR) assumption necessary for valid application of MI.

To implement the MI for primary efficacy testing, 20 imputed data sets will be constructed. If the pattern of missing data is not monotonic, a fully conditional (FCS) approach as implemented in SAS PROC MI (SAS Institute)⁴ will be utilized. If the pattern of missing data is monotonic, a regression approach may be used. The MI model will include age, BMI, sex, and the number of days since first COVID-19 symptom (≤ 5 or > 5 days), as well as temperature at Day 7 and 14 taken at the clinic. Should the pattern of missing data be non-monotonic, an FCS model will be utilized. The estimated treatment group difference and standard error will be determined for each imputed data set and combined using Rubin's rule as implemented in SAS PROC MIANALZE. The final treatment group difference will be the average of the multiple imputed datasets. The standard error, p-value, and width of the confidence interval will account for both within and between imputation error.

The validity of the MI depends on the assumption of Missing at Random (MAR). MAR means that the likelihood of missingness does not depend on the unobserved event status. A tipping point analysis will be performed to evaluate the robustness of this assumption. First a completer's analysis will be performed in which only subjects with complete endpoint status (that is, did not withdraw early or discontinue) are included. Then, all subjects with missing data are included in the analysis varying the numbers of subjects assumed to have experienced the event in both groups separately. This analysis includes the worst-case scenario in which all missing treated subjects are assumed to have experienced the event and all placebo subjects are assumed to have not experienced the event. It also includes the best-case scenario, in which all missing treated subjects are assumed to have not experienced the event and all placebo subjects are assumed to have experienced the event. All other scenarios are similarly evaluated. Assuming superiority has been demonstrated, the percentage of scenarios in which the results change from rejecting the null hypothesis to not rejecting the null hypothesis is determined.

If this percentage of scenarios in which study conclusions change is small (for example, less than 20%), then the superiority conclusion has been shown to be robust with regard to missing data.

As requested by FDA, an additional sensitivity will be provided in which all missing data are treated as failures.

If an exact test is necessary for the primary endpoint due to expected cell counts < 5 in either group, only the tipping point analysis based on the exact tests will be provided.

³ Rubin DB and Schenker N. Multiple imputation in health-care databases: an overview and some applications. *Statistics in Medicine* 10: 585-598, 1991.

⁴ Version 9.4, SAS Institute Inc, Cary, NC

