7.1 Description of Overall Study Design and Plan

This is a randomized, double-blind, placebo-controlled study of camostat mesilate in ambulatory outpatients with confirmed COVID-19 with at least one risk factor for severe illness. Subjects will be randomized in a 2:1 ratio of camostat mesilate:placebo. Approximately 300 subjects are planned to be enrolled (200 subjects to camostat mesilate and 100 subjects to placebo). Subjects will be treated with camostat mesilate 200 mg orally QID for 14 days and receive local SOC in addition to study drug. Subjects in the control arm will receive 2 placebo tablets orally QID for 14 days, as well as local SOC. All subjects will be followed until Day 28. Subjects will complete a symptom eDiary daily from Day 1 (first dose of study drug) through Day 15. Subjects will be coming into the clinic for assessments on Day 1, Day 7 and Day 15. Mid-turbinate nasal samples will be obtained at Screening, Day 7 and Day 15. Instructions for obtaining proper nasal samples will be provided. Subjects who withdraw from the study prior to completion of the 14-day

treatment period will be asked to return for an Early Termination visit for blood draws and a mid-turbinate swab collection. On Day 28 (end of study), a study team member will record subject disposition.

Figure 1 presents the study design.

Figure 1. Study Schematic

Abbreviations: COVID-19 = coronavirus disease 2019; SOC=standard of care.

^a The Screening/Baseline and Day 1 visit assessments can be done on the same day.

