4.1.3 Testing of Primary Efficacy Hypothesis

Primary results will include the numbers and percentages of subjects in each treatment group requiring COVID-19 related hospitalization/ER visit or who died due to any cause within 28 days of randomization.

As noted in the next section, the study is statistically powered by assuming that $\pi_{cm} = 0.15$ and $\pi_{pl} = 0.30$ and the number of subjects to be randomized are 186 and 93, in the active and placebo arms, respectively. Consequently, the expected number of subjects to experience the event is nearly 28 for both arms, with 158 and 65 subjects in the active and placebo arms, respectively, not expected to experience the primary endpoint. Therefore, an unadjusted chi-squared test (or exact test, if expected cell counts are < 5 in either group) will be used to test the primary efficacy hypotheses using a two-sided type 1 error of 0.05. Superiority will be concluded if $p < 0.05$ and the proportion of subjects experiencing the event is smaller among subjects randomized to the active treatment. This is tantamount to specifying a one-sided type 1 error rate of $\alpha = 0.025$.

In addition to determining the p-value for the primary efficacy hypothesis, results will also be expressed in terms of a two-sided normal based (asymptomatic) 95% confidence interval estimating the treatment group difference in 28-day COVID hospitalization or death. The upper bound of the confidence interval will be interpreted as the smallest treatment effect consistent with the study results.

If the expected number of events in either group is less than five (5), a Fisher's exact test and exact binomial intervals will be provided.

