4.1.4 Sample Size Determination for the Primary Efficacy Hypothesis

Sample size determination assumed event rates of 15% and 30% in the active and placebo groups, respectively, 2:1 randomization, and a two-sided type 1 error rate of $\alpha=0.05$. Under these assumptions, an adjusted chi-square test will have 80% power for sample sizes of 186 and 93 in the investigational and placebo arms, respectively (total sample size = 279). The sample size is increased by approximately 7.5% to allow for up to 200 and 100, respectively, to account for loss-to-follow-up.

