4.1.6 Handling of Baseline Differences

Group differences in baseline characteristics will be evaluated. Analyses will be performed to evaluate the treatment effect controlling for baseline covariates found to have clinically meaningful baseline differences. Clinically meaningful will be determined by the Sponsor Study Safety Monitor or Primary Investigator. This will be done using a generalized linear model with parameters estimated using SAS PROC GENMOD with distribution set to *binomial* and link set to *logit*. The adjusted probabilities and their standard errors are determined on the probability scale using the *ilink* option in a *lsmeans* statement with a *diff* option. This statement produces a test for the treatment group difference controlling for other covariates in the model. The model will include treatment group and each identified covariate one-at-a-time. The standard error on the probability scale for the difference in event rates will be determined as the square root of the sum of the treatment group specific squared standard errors and used in the determination of the 95% CI.

As requested by FDA, multivariable analyses will be provided to the degree that sample size and number of observed events in each group allow. It is understood that a total of 10 events per covariate is necessary for this modeling approach, which limits the number of covariates the model can support. The full model will consist of age, BMI, sex, and the number of days since first COVID-19 symptom (≤ 5 or > 5 days), in addition to treatment group (sample size permitting). In addition to the full model, a forward stepwise procedure will be used to identify a set of covariates that each provide some independent association with the primary outcome.

The totality of evidence (i.e., the clinical and statistical interpretations) will provide support for decision making regarding Phase III investigation.

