4.2 ANALYSES OF SECONDARY EFFICACY ENDPOINTS

4.2.1 Survival/Mortality

The overall survival rate (the proportion of randomized subjects who survive up to Day 15 and Day 28) will be summarized using the same approach as the primary outcome.

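### The imputation model for the primary test does not list treatment group, so imputed outcomes follow a risk common to both arms and the estimated effect shrinks toward zero

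*SAP*

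**What the plan says.** SAP 4.1.7 makes multiple imputation (20 data sets) the primary ITT efficacy test, with the completers and tipping-point analyses as sensitivity analyses. The imputation variables are given as "The MI model will include age, BMI, sex, and the number of days since first COVID-19 symptom" (dichotomized at 5 days), "as well as temperature at Day 7 and 14 taken at the clinic". Each completed data set then yields a treatment difference and standard error, which are combined by Rubin's rules. Treatment group is not among the variables, and neither document says that imputation is done separately by arm. The protocol (section 13) leaves missing data to the SAP, so nothing there fills the gap.

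In SAP 4.1.6, immediately before, the same four baseline covariates define the full adjusted outcome model, and there treatment is named: "in addition to treatment group (sample size permitting").

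Two related points:

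- **Visit day.** The second temperature is described as a Day 14 clinic measurement, but protocol 7.1 says "Subjects will be coming into the clinic for assessments on Day 1, Day 7 and Day 15". SAP 4.3.7 takes Day 14 temperature from the e-diary and lists Day 15 among the clinic or phone measurements.
- **Other endpoints.** Survival (SAP 4.2.1) "will be summarized using the same approach as the primary outcome", and SAP 4.2.2 sends viral shedding to the primary endpoint's approach.

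**The concern.** An imputation model has to contain every variable whose association with the outcome will be estimated afterwards. Here that variable is treatment arm. If it is left out, the model treats outcome and arm as unrelated given the covariates, and the imputed values carry little or none of the drug's effect. The completed data mix observed subjects, who show the effect, with imputed subjects, who do not.

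This bias arises even when the data are missing at random, because the fault lies in the imputation model and not in the missingness mechanism. It affects the primary estimate, its confidence interval and its p-value. Rubin's variance also stops matching the true sampling variance, because the analysis estimates a parameter that the imputation model has set to zero. A trial sized at 80% power would be tested with less.

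There is also a risk to interpretation. A gap between the imputed and completers results could be read as evidence against missing at random when the imputation model itself produced it.

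**Working it through.** **Inputs**

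- Test: SAP 4.1.3, "will be used to test the primary efficacy hypotheses using a two-sided type 1 error of 0.05".
- Rates and allocation: SAP 4.1.4, "Sample size determination assumed event rates of 15% and 30% in the active and placebo groups, respectively, 2:1 randomization". Placebo p = 30%, camostat c = 15%.
- Size: SAP 4.1.4, "an adjusted chi-square test will have 80% power for sample sizes of 186 and 93", a total of 279, raised to 200 and 100.
- Planned loss: 300 − 279 = 21, and 21/300 = 7.0% of those randomized. The SAP's 7.5% is 21/279.
- Imputations: 20 (SAP 4.1.7).

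**Step 1: reproduce the plan's figure.** Exact two-sided Fisher power is 80.2% at 186/93, so the SAP's 80% is reproduced. It is also 80.2% at the protocol's 183/92. At 186/93 the continuity-corrected chi-square gives 78.3% and the uncorrected test 82.4%.

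Rubin's rules use the unpooled standard error of the risk difference. With 186/93 this is √(0.30×0.70/93 + 0.15×0.85/186) = 0.0543, so power is about Φ(0.15/0.0543 − 1.96) = Φ(0.80), or 79%. This is why the benchmark for the imputed test below is near 80% and not 82%.

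**Step 2: expected difference when arm is left out.** Let m_pl and m_cm be the missing fractions, with missingness unrelated to outcome within arm, and let p₀ be the pooled observed risk. Then

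expected difference = (p − c) − m_pl(p − p₀) − m_cm(p₀ − c).

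Whenever c < p, p₀ lies between them. Both subtracted terms are then at least zero, so the bias is toward zero. With equal missingness m the expression reduces to (1 − m)(p − c).

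Pooled risk: (30% + 2×15%)/3 = 20%. At m = 7%:

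- placebo: 0.93×30% + 0.07×20% = 29.3%
- camostat: 0.93×15% + 0.07×20% = 15.35%
- difference: 29.3% − 15.35% = 13.95 points, a bias of 1.05 points or 7% of the effect.

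Unequal missingness (assumed; camostat/placebo) gives 14.2 points at 10%/3%, 13.8 at 3%/10% and 13.8 at 12%/6%.

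**Step 3: power by simulation.** Trials of 200/100 were simulated with 20 imputations drawn from beta posteriors (pooled or arm-specific), risk difference with unpooled variance, and Rubin's rules with a t reference. One run used 8,000 trials per setting and another 20,000. Where both covered a setting, the range is shown. Only the 7% row comes from the plan; the other missing fractions are assumptions.

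| Missing | Difference, arm left out (formula) | Power, arm left out | Power, arm included |
|---|---|---|---|
| 5% | 14.25 points | not run | not run |
| 7% | 13.95 points | 75.9–76.3% | 79.6–80.0% |
| 10% | 13.5 points | 72.4% | 78.3% |
| 15% | 12.75 points | 65.3–65.9% | 75.3–75.6% |
| 20% | 12.0 points | not run | not run |

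At 7% the simulated mean difference was 13.96 points with arm left out and 15.0 with arm included. The completers analysis had 79.6% power, so the primary analysis as written does worse than its own sensitivity analysis.

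**Step 4: variance.** With arm left out, the mean Rubin standard error at 7% was 0.0535 against an empirical SD of 0.0510 (0.0503 in the larger run). At 15% it was 0.0552 against 0.0482. With arm included the two nearly agree: 0.0540 and 0.0547 at 7%.

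**Step 5: no true effect (20% in both arms).** There is no bias. Rejection in favor of camostat, nominally 2.5%, was 1.6% at 7% missing and 0.9% at 15% with arm left out, against 2.3% and 2.0% with arm included.

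**The case against.** The strongest reply is that the list may not be exhaustive. The SAP says what the model will include, not that it includes nothing else, and the list also omits the endpoint itself, which any model imputing it must contain. A programmer might add treatment. That is possible, but the primary test should not depend on it. The neighboring section names treatment beside the same four covariates, and a reader following 4.1.7 literally would leave it out.

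Second, the effect at the planned loss is limited: 1.05 points against a standard error of about 5.4 points, roughly 0.2 of a standard error. False-positive risk falls rather than rises. Protocol 8.5 also commits to following discontinued subjects to Day 28, so stopping treatment need not mean a missing outcome. All of this stands. It limits the size of the problem and leaves its direction unchanged.

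Third, the simulation draws from a marginal pooled risk, whereas the SAP conditions on covariates and post-baseline temperatures. Temperatures could carry some of the drug effect, so the figures lie toward the upper end. Subjects lost early will often have no such temperatures.

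Fourth, the completers, best-case, worst-case and all-missing-as-failure results appear in the same table as the imputed result, and the tipping-point analysis is planned too. They would give a reader some warning, but they do not correct the primary test.

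On the side points, the carry-over to survival is weak: with few deaths, the exact-test rule in 4.1.7 would drop imputation. Viral shedding is the more exposed endpoint, though extending imputation to it is a reading of 4.2.2 and not an explicit statement. The ±1 day window means that some Day 15 visits fall on Day 14, so that item is a labeling inconsistency.

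**Conclusion.** The concern holds. As written, the primary multiple imputation draws missing outcomes without regard to arm, and the estimated effect is pulled toward zero by about the missing fraction. At the plan's 7% loss and its own event rates, this costs 1.05 of 15 points and about 4 points of power (about 76% instead of about 80%). At an assumed 15% loss it costs 2.25 points and about 10 points of power. Rubin's standard error is also too large.

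The figures assume that missingness is unrelated to outcome within arm and that the listed covariates and temperatures carry little information about arm. Type I error is not inflated. The problem does not arise for an endpoint if the exact-test fallback replaces imputation. It should be corrected before unblinding because it affects the pre-specified primary estimate, interval and p-value.

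**What to change.** In SAP 4.1.7, state that the imputation model includes treatment group and the primary endpoint alongside the listed covariates, or that imputation is carried out separately within each arm. Replace the Day 14 clinic temperature with the scheduled Day 15 clinic temperature. In SAP 4.2.1 and 4.2.2, say whether imputation applies to survival and viral shedding and, if so, use the same corrected model.

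The cost is a sentence or two in the SAP and one variable (or a by-arm statement) in the PROC MI call. No design, sample-size or data-collection change is needed.

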COVID-19 is diagnosed by using reverse transcriptase-polymerase chain reaction (RT-PCR) from a nasopharyngeal swab sample. The sensitivity of this assay is high but not 100%; therefore repeat testing is important if the person continues to exhibit symptoms, has knowingly been exposed, or lives in an area where there are a high number of COVID-19 cases ([Gandhi et al, 2020](#)).

The most common symptoms of a mild to moderate COVID-19 infection are fever, cough, sore throat, malaise, and myalgia. Anorexia, nausea, diarrhea, anosmia, and ageusia are often reported. Dyspnea may occur (usually 5 to 8 days after symptom onset) and is suggestive of more severe disease, often a precursor to hospitalization. Dyspnea can occur in patients with moderate disease but the oxygen saturation is usually at least 94% on room air ([Gandhi et al, 2020](#)). Importantly, clinical deterioration typically does not occur until more than 5 to 7 days following symptom onset, suggesting there is a window of opportunity for antiviral therapy early in the infection prior to the subsequent onset of severe systemic inflammation.

Certain comorbid conditions render a person more susceptible to contracting COVID-19 and contribute to worsening of the disease to a more severe version. These conditions include: age ≥ 65 years, cardiovascular disease, chronic lung disease, hypertension, diabetes, obesity, and diseases that weaken the immune system ([Gandhi et al, 2020](#)).

Patients with mild or moderate COVID-19 are usually instructed to recover at home, where they can be isolated, observed, monitored, and receive supportive care. However, some patient's conditions may deteriorate, especially those with comorbid conditions, which most often happens a week after onset of symptoms. These patients should be monitored closely. Patients with mild to moderate disease are able to monitor their own oxygen saturation levels if they are given a pulse oximeter ([Gandhi et al, 2020](#)).

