2.4 RANDOMIZATION

Subjects will be randomized in a 2:1 ratio of Camostat mesilate: placebo. Approximately 300 subjects are planned to be enrolled (200 subjects to Camostat mesilate and 100 subjects to placebo).

One global computer generated, blocked randomization list with 2/3's of the assignments will be to Camostat mesilate and 1/3 to placebo, in random order. Randomization block sizes will randomly vary in size 3 and 6. Labeling will be randomly varied as an additional masking feature.

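### The primary multiple imputation lists neither event-free follow-up time nor treatment group, so late losses are imputed at roughly the full 28-day risk and the risk difference is biased in a direction the documents do not determine

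*SAP*

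**What the plan says.** SAP 4.1.7 makes multiple imputation the primary handling of subjects lost before Day 28: 20 data sets, combined by Rubin's rules. The predictors are stated as "The MI model will include age, BMI, sex, and the number of days since first COVID-19 symptom" (two classes, split at 5 days), "as well as temperature at Day 7 and 14 taken at the clinic". Date of last contact, days followed event-free and treatment group are not named, and imputing separately by arm is not mentioned. By contrast, SAP 4.1.6 names treatment group explicitly in the adjusted outcome model.

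The clinic schedule in protocol 7.1 is "Subjects will be coming into the clinic for assessments on Day 1, Day 7 and Day 15". SAP 4.3.7 places clinic or telephone temperatures on Days 15, 21 and 28, and treats Day 14 as the last eDiary maximum.

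SAP 4.1.7 adds a completers analysis, a tipping-point grid over all event counts among missing subjects in each arm, and an analysis counting all missing as failures. SAP 3.2 and 4.2.2 plan a Kaplan-Meier and log-rank analysis of time to the same event.

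**The concern.** The endpoint is absorbing: once a subject is hospitalized, visits the emergency room or dies, the outcome is known. The subjects left to impute are therefore those still event-free when last seen. Someone event-free on Day 21 has one week of risk left, but a model without follow-up time draws the outcome from something close to the whole 28-day risk. Even if drop-out is pure chance, having the event makes a subject less likely to be missing. The missing-at-random assumption on which SAP 4.1.7 relies therefore fails, given the listed predictors.

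Leaving out treatment group is a separate fault. It pulls both arms' imputed subjects towards a common risk and shrinks any real difference. Both faults act on the primary ITT estimate and its p-value.

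**Working it through.** **Inputs.** Test: "using a two-sided type 1 error of 0.05" (SAP 4.1.3). Rates: "Sample size determination assumed event rates of 15% and 30% in the active and placebo groups, respectively" (SAP 4.1.4). Allocation: "Subjects will be randomized in a 2:1 ratio of Camostat mesilate: placebo" (SAP 2.4). Size: "an adjusted chi-square test will have 80% power for sample sizes of 186 and 93" (SAP 4.1.4), raised to 200 and 100 for loss.

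**The plan's own figures.** Exact binomial enumeration at 186 and 93 gives power of 80.2% (Fisher), 78.9% (continuity-corrected chi-square) and 83.0% (uncorrected). The protocol's 183 and 92 with Fisher gives 80.2%. Both sample sizes reproduce within two points for the corrected and exact tests. The loss allowance is 1 − 279/300 = 7.0%, or 14 camostat and 7 placebo subjects.

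**Remaining risk at loss.** With 28-day risk p and a share F(t) of events occurring by day t, a subject event-free at t has remaining risk p(1 − F(t))/(1 − pF(t)). The documents give no event-time distribution, so two are assumed, with losses uniform over 28 days:

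| Event timing (assumed) | Mean remaining risk, camostat / placebo | If event-free on Day 21 |
|---|---|---|
| Uniform | 7.9% / 16.8% | 4.2% / 9.7% |
| Front-loaded (Weibull, shape 1.3, scale 7 days, median about Day 5) | 3.7% / 7.9% | 0.2% / 0.6% |

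Imputing at the full risk gives 14 × 0.15 + 7 × 0.30 = 4.2 events. The remaining risk warrants 14 × 0.037 + 7 × 0.079 = 1.1 to 14 × 0.079 + 7 × 0.168 = 2.3.

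**Effect on the risk difference.** Let a share d of an arm be lost, independently of outcome, when a fraction f of its 28-day events has occurred. Then:

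- observed events E = p(1 − d) + dpf
- missing M = d(1 − pf)
- estimated arm risk = E + M × imputed risk

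The imputed risk is one of:

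- (a) the arm's own observed risk E/(1 − M)
- (b) the observed risk pooled over arms at 2:1, which is the literal reading of the list
- (c) the remaining risk p(1 − f)/(1 − pf)

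Worked case, d = 7% in both arms, f = 0.9:

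- Camostat: E = 0.1395 + 0.00945 = 0.14895; M = 0.06055; own risk 0.14895/0.93945 = 0.1586.
- Placebo: E = 0.279 + 0.0189 = 0.2979; M = 0.0511; own risk 0.2979/0.9489 = 0.3139.
- (a) 0.3139 − 0.1586 = 15.5 points.
- (b) Pooled risk (2 × 0.14895 + 0.2979)/(2 × 0.93945 + 0.9489) = 0.2107. Placebo is 0.2979 + 0.0511 × 0.2107 = 0.3087 and camostat 0.14895 + 0.06055 × 0.2107 = 0.1617. The difference is 14.7 points.
- (c) 15.0 points.

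Placebo minus camostat, in points, against a truth of 15.0:

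| Loss, camostat / placebo | f | (a) arm in model | (b) as listed |
|---|---|---|---|
| 7% / 7% | 0 to 1 | 15.0 to 15.6 | 13.95 to 14.78 |
| 15% / 15% | 0.9 | 16.21 | 14.32 |
| 10% / 5% | 0.9 | 14.72 | 13.93 |
| 5% / 10% | 0.9 | 16.44 | 15.40 |

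Option (c) returns 15.0 in every row. At f = 0 option (a) is unbiased, so the 1.05-point deficit under (b) there comes entirely from omitting treatment group.

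**No true effect.** Equal loss gives zero bias at every f. With 15% risk in both arms and f = 0.9, loss of 5% and 10% gives a spurious 0.61 to 0.66 point towards camostat when placebo loses more, and 0.62 to 0.66 against it when camostat loses more.

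**The case against.** The effect is small at the planned loss. The standard error of the difference at 200 and 100 is √(0.15 × 0.85/200 + 0.30 × 0.70/100) = 5.2 points, so 0.6 point is 0.6/5.2 = 0.12 of a standard error and 1.05 points is 0.20. Timing is assumed throughout. The protocol's remark in 5.1.1 that "clinical deterioration typically does not occur until more than 5 to 7 days following symptom onset" counts from symptom onset, not from randomization, so it does not fix f. The predictor list may not be exhaustive, protocol 8.5 aims to follow discontinued subjects to Day 28, and the tipping-point grid already contains the right event counts.

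All of this stands and limits the consequence. It does not repair the primary estimate. Completers shares the upward bias in each arm's risk, counting all missing as failures goes further that way, and the grid only describes robustness.

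A reader might infer more in four ways, none supported:

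- **That camostat's benefit is overstated.** This needs treatment group in the model with equal loss, or heavier placebo loss with enough events before loss. As listed, with equal loss, the benefit is understated; heavier camostat loss understates it under both readings.
- **That the false-positive rate is generally inflated.** With no effect and equal loss the bias is zero.
- **That the model uses nothing after baseline.** It includes two post-baseline temperatures, though neither records event-free time.
- **That the Day 14 temperature causes the problem or destabilizes the imputation.** The ±1 day window in protocol Table 1 can put the Day 15 visit on Day 14. The label is a mismatch, unrelated to follow-up time, and no instability has been shown.

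**Conclusion.** The point holds in this form: the listed imputation model omits event-free follow-up time and treatment group, so imputed risk is too high in each arm and the primary risk difference is biased, with a sign that depends on the model actually fitted and on the pattern of loss. At 7% equal loss the shift runs from 1.05 points under to 0.6 point over a true 15.0. At 5% and 10% loss, with 90% of events before loss, it runs from about 1.1 under to 1.4 over. These are large-sample expectations that assume loss independent of outcome and ignore what the other predictors contribute. Loss rates other than 7%, and all event and loss timing, are assumptions. On the literal list, the missing treatment term is the larger fault at equal loss. The matter is worth correcting before unblinding, but at the planned loss it is unlikely by itself to decide the trial's conclusion.

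**What to change.** In SAP 4.1.7:

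1. Name treatment group in the imputation model, or state that imputation is run separately by arm.
2. Impute only the remaining risk from last event-free contact to Day 28. One way is sequential logistic imputation of an event indicator for each interval (to Day 7, 15, 21 and 28) among subjects still event-free. Another is to draw from the arm-specific Kaplan-Meier conditional risk over that period.
3. Change the temperature variables to the Day 7 and Day 15 clinic visits, or say explicitly if the Day 14 eDiary value is meant.

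The cost is SAP wording and modest programming. No new data are needed, because the time-to-event analysis already requires these dates. The drawback is few events in the late intervals, so the SAP should give a rule for merging them.
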